3. PLANNED ANALYSES

3.1. Final Analyses

The final planned primary analyses will be performed after the completion of the following sequential steps:

1. All subjects have completed the study as defined in the protocol.

- 2. All required database cleaning activities have been completed and final database release has been declared by Data Management.
- 3. All decisions on exclusion of data from PP analyses based on the PDMP will be agreed prior to releasing the randomization codes (See Section 10.1 for details).
- 4. All criteria for releasing the randomization codes have been met.
- 5. Randomization codes have been distributed according to RandAll NG procedures.
- 6. Database freeze has been declared by Data Management.

Population	Definition / Criteria	Analyses Evaluated
All Subjects Enrolled (ASE)	 All subjects for whom a record exists on the study database, including screen failures and any subject who was not screened but experienced a serious adverse event (SAE) between the date of informed consent and the planned date of the Screening Visit. Displays for this population will not be split by treatment. 	 Subject disposition Reasons for withdrawal prior to randomization Inclusion/exclusion/ran domization criteria deviations for non- randomized subjects SAEs for screen and run-in failures and randomized subjects
Intent-To-Treat (ITT)	 All randomized subjects, excluding those who were randomized in error, who received at least one dose of study medication. A subject who is recorded as a screen or run-in failure and also randomized will be considered to be randomized in error. Any other subject who receives a randomization number will be considered to have been randomized. Displays will be based on the treatment to which the subject was randomized. 	 Study population Primary efficacy Other efficacy Safety
Per-Protocol (PP)	 All subjects in the ITT Population who were not identified as full protocol deviators. Subjects with partial protocol deviations considered to impact efficacy will be included in the PP Population but will have their data excluded from the PP analysis from the time of deviation onwards. Subjects with time-point specific or period specific protocol deviations will be included in the PP population but will have the data affected excluded from the PP analysis. Protocol deviations that would exclude subjects from the PP population or subject data from PP analysis are defined in Appendix 1 (Protocol Deviation Management and Definition for Per-Protocol Population). The decision to exclude a subject from the PP 	Primary efficacy

4. ANALYSIS POPULATIONS

Population	Definition / Criteria	Analyses Evaluated
	population will be made prior to releasing the randomization codes.Displays will be based on the treatment to which the subject was randomized.	
Inhaler Naive (IN)	 All subjects in the ITT population who have not used either Ellipta or Respimat for 6 months prior to inhaler evaluation (Visit 2 or Visit 5). This population will be used for all Inhaler assessment displays. 	

NOTES :

 Please refer to Appendix 13: List of Data Displays which details the population to be used for each displays being generated.

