Any history of allergy or hypersensitivity to any anticholinergic/muscarinic receptor antagonist, sympathomimetic, lactose/milk protein or magnesium stearate.

[8] Antimuscarinic effects:

Subjects with medical conditions such as narrow-angle glaucoma, urinary retention, prostatic hypertrophy, or bladder neck obstruction should be excluded unless, in the opinion of the study physician, the benefit outweighs the risk.

[9] Hospitalization:

Hospitalization for COPD or pneumonia within 12 weeks prior to Visit 1. **Pneumonia** and/or moderate or severe COPD exacerbation that has not resolved at least 14 days prior to Screening (V1) and at least 30 days following the last dose of oral/systemic corticosteroids (if applicable).

Other respiratory tract infections that have not resolved at least 7 days prior to Screening (V1).

[10] Lung Resection:

Subjects with lung volume reduction surgery (including procedures such as endobronchial valves) within the 12 months prior to Screening (V1).

[11] **12-Lead ECG:**

The Investigator will determine the clinical significance of each abnormal ECG finding in relation to the subject's medical history and exclude subjects who would be at undue risk by participating in the trial. Subjects with the following abnormalities are excluded from

participation in the study:

- Atrial fibrillation with rapid ventricular rate >120 bpm
- Sustained or nonsustained ventricular tachycardia
- Second degree heart block Mobitz type II or third degree heart block (unless pacemaker or defibrillator had been inserted)

[12] Medication Prior to Spirometry:

Unable to withhold albuterol/salbutamol for the 4 hour period required prior to spirometry testing at each study visit.

[13] Medications Prior to Screening:

Use of the following medications according to the following defined time intervals prior to Screening (Visit 1):

Medication	Time interval
Depot corticosteroids	12 weeks
Systemic, oral or parenteral corticosteroids1	6 weeks
Antibiotics (for lower respiratory tract infection)	6 weeks
LABA/Inhaled Corticosteroid (ICS) combination products	30 days
ICS	30 days
Phosphodiesterase 4 (PDE ₄) Inhibitor (roflumilast)	14 days
Inhaled long acting beta ₂ agonists (LABAs):	
-salmeterol, formoterol	48 hours
-olodaterol, indacaterol, vilanterol	14 days
Long-acting muscarinic antagonists (LAMAs): tiotropium,	7 days
aclidinium, glycopyrronium, umeclidinium	
LAMA/LABA combination products	Apply whichever mono
	component has the longest
	washout

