7.1. Time and Events Table

		Screen/Run-in		Treatment 1			Wash-	Treatment 2			Post-Treatment	
							Out					
Visit		0	1	2	3	4		5	6	7	EW Visit ²	Follow up
		Prescreen ¹	(Screen)	(Rand)								Contact ¹¹
Treatment Day			14 ± 3 days prior to Visit 2	1 ±3 days	28 ±3 days	56 ±3 days	21 days ± 3 days	1 21 ± 3 days after V4	28 ± 3 days after V5	56 ± 3 days after V5		7 ± 3days after V7 or EW Visit
Week			-1	N/A	4	8		N/A	4	8		
Screen /	Written informed consent	Х										
Baseline	Demography	Х										
	Medical/COPD history		Х									
	Smoking history/status		Х							Х	Х	
	Smoking cessation counselling		Х							Х	Х	
	Verify Inclusion/exclusion criteria		Х									
	Concomitant medication assessment	Х	Х	Х	Х	Х	Х	Х	Х	Х	Х	X
	Verify Randomization criteria			Х								
	Physical examination		Х							Х	Х	
	Screening 12-Lead ECG		Х									
	Screening spirometry (including post- bronchodilator testing) ³		Х									
	mMRC dyspnea scale		Х									
	Training on use of inhalers ¹³			Х				Х				
	Training in the use of eDiary and eMDI		Х									
	Register visit IVRS	X	Х	Х	Х	Х	Х	Х	Х	X	X	X

2015N256437_00

CONFIDENTIAL

Visit		Screen/	een/Run-in		Treatment 1			Treatment 2			Post-Treatment	
		0 Prescreen ¹	1 (Screen)	2 (Rand)	3	4		5	6	7	EW Visit ²	Follow up Contact ¹¹
Treatment Day			14 ± 3 days prior to Visit 2	1 ±3 days	28 ±3 days	56 ± 3 days	21 days ± 3 days	1 21 ± 3 days after V4	28 ± 3 days after V5	56 ± 3 days after V5		7 ± 3days after V7 or EW Visit
Week			-1	N/A	4	8		N/A	4	8		
Efficacy/	Pre dose Spirometry (FEV ₁ , FVC and IC) ⁴			Х				Х				
Inhaler Evaluations	Trough Spirometry (FEV ₁ , FVC and IC) ⁵				Х	Х			Х	Х		
	CAT ¹²		Х	Х	Х	Х		Х	Х	Х		
	EXACT-PRO (14 item questionnaire)					• • • • • • • • • • • • • • • • • • • •						
	Inhaler Ease of use assessment			Х				Х				
	Inhaler Errors assessment ¹³			Х				Х				
Safety	Adverse event assessment ⁶		Х	Х	Х	X	X	Х	X	Х	Х	X
	COPD exacerbation assessment	X	Х	Х	Х	X	X	Х	X	Х	Х	X
	Urine pregnancy test ⁷		Х	Х				Х		Х	Х	
	Observed dose in clinic ¹⁴				Х				Х			
Medication/ Supplies	Dispense rescue albuterol/salbutamol ⁸ with eMDI		X	Х	X	X		X	X	Х		
	Collect rescue albuterol/salbutamol ⁹ with eMDI			X	X	X		X	X	Х	X	
	Dispense period 1 study medication			Х	Х							
2015N256437 00

CONFIDENTIAL

		Screen/	Run-in		Treatment	1	Wash- Out		Treatment	2	Post-Tr	eatment
Visit		0 Prescreen ¹	1 (Screen)	2 (Rand)	3	4		5	6	7	EW Visit ²	Follow up Contact ¹¹

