7.3. Efficacy

7.3.1. Spirometry

Spirometry measurements will be obtained using spirometry equipment that meets or exceeds the minimal performance recommendations of the ATS [Miller, 2005]. All sites will use standardized spirometry equipment provided by an external vendor.

All subjects will have spirometry performed at Screening and at Visits 2, 3, 4, 5, 6, and 7 during the treatment period. For FEV_1 and FVC determinations, at least 3 acceptable spirometry efforts (with no more than 8) should be obtained. Acceptable spirometry efforts should have a satisfactory start of test and end of test (i.e. a plateau in the volume time curve) and be free from artifacts due to cough, early termination, poor effort, obstructed mouthpiece, equipment malfunction, or other reasons [Miller, 2005].

The largest FEV_1 and FVC from the 3 acceptable efforts should be recorded, even if they do not come from the same effort.

Spirometry for FEV₁, and FVC assessments that is not obtained as follows will be considered a protocol deviation:

- Started between 6:00AM and 11:00AM.
- After withholding albuterol/salbutamol (all visits) ≥4 hours and after withholding short-acting inhaled anticholinergics taken during washout for ≥4 hours prior to Visit 5
- At Visit 1, after withholding COPD medications as specified in the exclusion criteria in Section 5.
- At Visit 3 and 6 after withholding the morning dose of study drug (note study drug will not be administered at visits 4 and 7).
- Pre dose assessments performed prior dosing

Subjects should refrain from smoking for 1 hour prior to each pulmonary function test.

On Day 1 of each treatment period (Visits 2 and 5 respectively), pre-dose spirometry measurements should be conducted 30 minutes and 5 minutes prior to dosing. Trough measurements on Weeks 4 (Visits 3 and 6) and Week 8 (Visits 4 and 7) of each treatment period should be done 23 hours and 24 hours after the previous day's dose of study medication. Any trough FEV₁ measurement collected outside 22.0-25.0 hours after the previous day's dose will be considered protocol deviations with data exclusion from the Per Protocol population analysis of trough FEV₁.

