7.4.4.2. Inhaler Errors

Inhaler errors will be assessed using the Inhalers Errors Checklist at Visit 2 and Visit 5 to assess the critical and overall (critical and non-critical) errors made by subjects with the ELLIPTA and Respimat inhalers.

The investigator (or designee)-administered inhaler errors checklist is based on the steps listed in the Patient Information Leaflets (PIL) for each inhaler. The proportion of subjects reported by the investigator or designee as making at least one critical error (defined as an error that is most likely to result in no or only minimal medication being inhaled) or overall error (includes a critical and non-critical error) will be evaluated in this study.

The inhaler errors checklist will be administered by the investigator or designee.

At Visit 2 and 5, the subject will prepare his or her inhaler for first use and selfadminister their first dose of the study medication in the clinic under the supervision of the investigator or designee. The subject will simply follow the instructions in the patient information leaflet without prior instruction on the day. Any errors (critical or noncritical) made by the subject while using the inhaler will be recorded by the investigator or designee. If the subject makes no errors, this will also be recorded. Any errors (critical or non-critical) made by the subject while using the inhaler will be recorded by the investigator or designee. If the subject makes no errors, this will also be recorded. The investigator or designee will demonstrate the correct use of the inhaler to the subject and will make sure the inhaler is loaded properly before the subject leaves the clinic.

Additional instructions for completion of the inhaler errors checklist are provided in the SPM.

7.4.5. Any Medical Problems Experienced and any Medications used to Treat those Medical Problems

Signs and symptoms of COPD included on the electronic diary card will not be considered AEs and will not be collected in the eCRF.

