	 The intent-to-treat (111) Population will comprise all randomized subjects, excluding those who were randomized in error, who received at least one dose of study medication. A subject who is recorded as a screen or run-in failure and also randomized will be considered to be randomized in error. Any other subject

Overview	Key Elements of the RAP
	who receives a randomization number will be considered to have been randomized. Displays will be based on the treatment to which the subject was randomized. This population will be the used for all efficacy and safety displays unless specified otherwise.
	• The Per Protocol (PP) Population will comprise all subjects in the ITT Population who do not have a full protocol deviation considered to impact efficacy. Receipt of a study treatment other than the randomized treatment will be considered a full protocol deviation. Subjects with partial protocol deviations considered to impact efficacy will be included in the PP Population but will have their data excluded from PP analyses from the time of deviation onwards. Subjects with time-point specific or period specific protocol deviations will be included in the PP population but will have the data affected excluded from PP analyses. This population will be used for the primary comparison between the treatments to determine NI. It will also be used for the primary comparison between treatments to assess superiority, assuming that the primary analysis on the PP population supports the conclusion of NI.
	• The Inhaler Naive (IN) population definition will comprise of all subjects in the ITT population who have not used either Ellipta or Respimat for 6 months prior to inhaler evaluation (Visit 2 or Visit 5). This population will be used for all Inhaler assessment displays unless stated otherwise.
Hypothesis	 The null hypothesis is that the difference in trough FEV₁ between treatment groups is less than or equal to a pre-specified non-inferiority margin Δ:
	$H_0: T_1 - T_2 \leq \Delta$
	The alternative hypothesis is that the difference between treatment groups is greater than the margin.
	$H_1: T_1 - T_2 > \Delta$
	where T_1 and T_2 are the treatment means for UMEC/VI 62.5/25 mcg and TIO/OLO 5/5 mcg, respectively.

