10.13.9. Non-ICH Listings

For all listings replace 'Centre ID'/'Inv. ID' header with 'Investigator at Centre'/'Inv. at Centre'. The CENTREID variable should be used for this.

Non-ICH : Listings									
No.	Population	IDSL / TST ID / Example Shell	Title	Programming Notes	Deliverable				
Study Pop	Study Population: Subject Disposition								
18.	ASE	IDSL - ES2	Listing of Reasons for Withdrawal – Subjects Randomized but Not in the ITT Population		SAC				
19.	ITT		Listing of the Follow-up Contact		SAC				
Study Population: Protocol Deviations									
20.	ITT		Listing of Exclusions from the Per-protocol Analysis		SAC				

Non-ICH : Listings								
No.	Population	IDSL / TST ID / Example Shell	Title	Programming Notes	Deliverable			
21.	ITT	IDSL – TA1	Listing of Treatment Misallocations	Change Centre ID to Investigator ID: xxxxxx And also Investigator at Centre: xxxxxx	SAC			
Study Pop	ulation: Treatm	ent						
22.	ITT		Listing of Overall Percentage Treatment Compliance		SAC			
23.	ITT	SP_L1	Listing of Subjects Who Discontinued Study Treatment		SAC			
Study Pop	Study Population: Medical Conditions & Concomitant Medications							
24.	ITT	IDSL – MH2	Listing of Medical Conditions		SAC			
25.	ITT		Listing of Family History of Cardiovascular Risk Factors		SAC			
26.	ITT		Listing of COPD History		SAC			
27.	ITT		Listing of Smoking History and Smoking Status		SAC			
28.	ITT	IDSL_ CM2	Listing of COPD Concomitant Medications		SAC			
29.	ITT	IDSL_ CM2	Listing of non-COPD Concomitant Medications		SAC			
30.	ITT	IDSL – CM6	Relationship between ATC Level 1, Ingredient and Verbatim Text for Non-COPD Medications		SAC			

Non-ICH : Listings								
No.	Population	IDSL / TST ID / Example Shell	Title	Programming Notes	Deliverable			
Study Population: Baseline Severity								
31.	ITT		Listing of GOLD Grade/Categories and Reversibility		SAC			
32.	ITT		Listing of mMRC Dyspnoea Scale at Screening		SAC			
Efficacy: Spirometry and IC								
33.	ITT		Listing of Derived FEV ₁ (L)		SAC			
34.	ITT		Listing of Derived FVC (L)		SAC			
35.	ITT		Listing of Derived IC (L)		SAC			
Efficacy: e	Diary endpoint	s						
36.	ITT		Listing of Derived Rescue Endpoints		SAC			
37.	ITT		Listing of E-RS Scores		SAC			
38.	ITT		Listing of Derived E-RS Scores		SAC			
QoL: CAT								
39.	ITT		Listing of CAT Scores		SAC			
Inhaler As	sessments							
40.	ITT		Listing of Errors on ELLIPTA Inhaler	Indicate IN pop flag	SAC			
41.	ITT		Listing of Errors on Respimat Inhaler	Indicate IN pop flag	SAC			

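### Can the Inhaler Naive population be formed at Visit 5, when subjects have just spent Period 1 on one of the two named inhalers?

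*SAP*

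**What the plan says.** The Inhaler Naive population exists only in the SAP; Table 1 of SAP section 2.1 records that the protocol had none. The synopsis, Table 1 and section 4 all define it as ITT subjects "who have not used either Ellipta or Respimat for 6 months prior to inhaler evaluation (Visit 2 or Visit 5"). On its use, the synopsis says: "This population will be used for all Inhaler assessment displays unless stated otherwise". SAP section 10.13.5 assigns it to Tables 2.41 to 2.43 (ease of use) and 2.44 to 2.46 (errors). Listings 40 to 43 are on ITT and carry the note "Indicate IN pop flag", without saying whether the flag is per subject or per device.

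On first handling of each device, Protocol section 7.4.4.2 says: "At Visit 2 and 5, the subject will prepare his or her inhaler for first use". One device is therefore evaluated at Visit 2 and the other at Visit 5. Ease of use has a p-value (SAP section 8.1.2.6) built from a within-subject comparison of the two ratings (SAP section 10.6.4). Inhaler errors are only summarised.

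**The concern.** The rule names both devices and both visits and says nothing about study treatment. A subject who reaches Visit 5 after Period 1 dosing has, by design, used one of the named devices within six months. Taken at face value, the Visit 5 part cannot be met, and a test that needs ratings from both visits would have no data.

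If the literal reading is set aside, a choice remains. The set could be subjects naive to both devices before Visit 2 (the both-device reading), or subjects naive to the device under evaluation, counted back from that device's own visit (the device-specific reading). These are not identical sets. Prior users can enter the trial: the exclusion criteria ask for 7 days off long-acting antimuscarinics, 14 days off "olodaterol, indacaterol, vilanterol", and 30 days off products containing an inhaled corticosteroid, all well short of six months.

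At stake is a p-value that SAP section 2.4 allows to be read at 0.05 once non-inferiority is shown, in an open-label trial where the analysis set is better fixed before results are seen.

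**Working it through.** **Inputs.** From the Time and Events Table (Protocol section 7.1): Visit 4 on day 56 ± 3; Visit 5 "21 ± 3 days after V4"; Visit 1 "14 ± 3 days prior to Visit 2". From Protocol section 7.3.1, on dosing: "note study drug will not be administered at visits 4 and 7". Six months is taken as about 182 days.

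**The plan's own figure.** 2 + 8 + 3 + 8 + 1 = 22 weeks, the participation time stated in Protocol section 4.2, so the schedule is read correctly.

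**First Period 1 dose to Visit 5.** With Visit 2 as Day 1, Visit 4 is 52 to 58 days later; adding 18 to 24 gives 70 to 82. Counting 56 ± 3 as elapsed days gives 53 to 59, hence 71 to 83. Together: 70 to 83 days.

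**Last planned Period 1 dose to Visit 5.** No dose is given at Visit 4, so the last is the day before: 1 + 18 = 19 to 1 + 24 = 25 days.

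Both intervals are far inside 182 days, so the literal rule fails everyone dosed in Period 1 at Visit 5.

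**If passing at either visit is enough.** Nobody dosed in Period 1 passes at Visit 5, so the set reduces to those who pass at Visit 2. That is the both-device reading, obtained from the text as it stands.

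**Where the two workable readings part.** Six months counted back from Visit 5 reach only 182 − 83 = 99 to 182 − 70 = 112 days before Visit 2. The band between that point and 182 days before Visit 2 is 182 − 112 = 70 to 182 − 99 = 83 days wide (70/182 = 38% to 83/182 = 46% of the window). For sequence 1 (Ellipta, then Respimat), with Visit 5 at 56 + 21 = 77 days after Visit 2:

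| Last pre-study use, days before Visit 2 | Both-device | Device-specific, paired test |
|---|---|---|
| Neither device | in | in |
| Respimat 150, no Ellipta | out | in (150 + 77 = 227 > 182) |
| Respimat 60, no Ellipta | out | out (60 + 77 = 137 < 182) |
| Ellipta 150 or 60, no Respimat | out | out |

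Sequence 2 mirrors this. Only the second row differs in the paired test. In the per-device displays the last row differs too: that subject would count for Respimat under the device-specific reading.

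**Number affected.** The documents give no rate of prior device use. An assumed 0 to 10% of subjects in the band would be 0 to 0.10 × 186 ≈ 19 of the 186 expected to have a Week 8 assessment. Nothing supports any particular value in that range.

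**Direction.** SAP section 10.6.4 codes the ordinal variable so that +1 means the second-period device was rated higher, in both sequences. Former users of the second device, kept by the device-specific reading, would tend to push the score the same way in both sequences. The planned test compares sequences, so such a shift cancels as far as these subjects are equally common in the two. No bias towards one device follows from the rule itself.

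**The case for a change.** The strongest case for a change is that the definition is defective on its face and nothing elsewhere repairs it. SAP section 10.6.4 derives the rating and error variables but not the population flag. One sentence would settle the matter, and a tested endpoint should not depend on an unstated derivation. There is also a data question. The protocol describes COPD medication history for 30 days before Visit 0 (section 6.10) and 3 months before Screening (section 7.2). The latter reaches 91 + 11 = 102 to 91 + 17 = 108 days before Visit 2, which is 74 to 80 days short of six months.

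The drafting criticism stands: the wording is loose, and a clearer sentence would do no harm. The rest carries less weight.

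- The one reading that breaks the analysis defeats the SAP's own table list, so no analyst would adopt it. Protocol section 6.10 also keeps study drug out of the concomitant medication record, so a flag built from that record would ignore Period 1 study use.
- Neither workable reading is clearly better. The both-device reading drops a prior user of one device from the other device's error table. It also overlooks non-study use of either device between Visit 2 and Visit 5. The device-specific reading keeps more subjects per table but lets entry to the paired test depend on sequence.
- The history shortfall is a query, not a fault. It compares the rule with concomitant-medication text, and the eCRF and the questionnaire instructions in the study procedures manual are not among the documents.

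**Conclusion.** No change to the plan is needed. The definition leaves a gap in the flag derivation, and any sensible analyst would close it by disregarding study treatment. The choice then left, between two defensible sets, is a fair trade-off, and the SAP synopsis already requires decisions on the final analysis to be made before database freeze.

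The effect is confined to ease of use, an endpoint in the Other category, and to descriptive error tables. The ITT listings keep every subject's inhaler data, and the trough FEV₁ analysis does not use this population. In the paired test the readings differ only for subjects whose last pre-study use of the Period 2 device lies between about 99 to 112 and 182 days before Visit 2, with no recent use of the Period 1 device. How many there are, and whether they would move the p-value, cannot be determined from the documents.

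This rests on six months being about 182 days, on visits falling within their windows, and on the eCRF holding enough device history to derive the flag, which the documents do not let a reader check.
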